Primary Outcome	
Our primary endpoints are:
 
 • Safety outcome measures will include treatment-emergent adverse events and abnormalities on standard laboratory tests. TEAE will be collected at 10 time points over 24 months of treatment in the Primary Cohort and collected at up to 7 time points over up to 18 months of treatment in the Open-label Cohort. Laboratory tests will be collected at 9 time points in the Primary Cohort and up to 6 time points in the Open-Label Cohort over the same respective periods. • Tolerability outcomes will be assessed via participant retention in the study and adherence to the study product regimen.
Secondary Outcomes	
Our secondary endpoint is: CoASY mRNA expression levels measured at 8 time points in the Primary Cohort and at up to 6 time points in the the Open-label Cohort.

Safety Assessments	
Treatment-emergent Adverse Events Baseline and at intervals throughout treatment (10 time points for the Primary Cohort and up to 7 timepoints for the Open-label Cohort)
 
 • Treatment-emergent adverse events will be classified according to Medical Dictionary for Regulatory Activities (MedDRA) terminology. • Severity of the AEs will be graded according to the NCI Common Terminology Criteria for Adverse Events, Version 4.0 
Clinical safety laboratory studies Baseline and at intervals throughout treatment (9 time points for Primary Cohort; up to 6 time points for the Open-label Cohort)
 
 • Complete metabolic profile (Includes Na^+, K^+, Cl^-, CO_2, BUN, Creat, Ca^{2+}, Glu, Alb, T. Protein, Alk Phos, T. Bili, AST, ALT) • Complete blood count with auto-differential • Creatine kinase (CK)
Tolerability Assessments	
Participant retention
 
 • During treatment and follow up • Number of participants retained in each arm at each of the follow up time points 
Participant adherence to study product regimen as measure of tolerability
 
 • During treatment and follow up • Mean percent of study product consumed

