Statistical Methods	
A modified Intention-to-Treat (ITT) analysis dataset of all randomized participants who consumed at least one dose of the study product. This is also the Safety Analysis dataset.
 
The Per-Protocol dataset will include participants who consume at least 75% of assigned study product.
 
General approach
 
The proposed study takes place over 28 months in the Primary Cohort. A screening period of up to 2 months will be followed by an initial 6-month double-blind, placebo-controlled parallel trial of the study product during which participants will be assigned to one of three dose groups [5mg/m², 15mg/m², 20mg/m²]; and then by a further 18 months of open label study during which all participants will be assigned a 15mg/m² dose. Participants will be followed for up to two months beyond the end of the open-label period. The primary data analysis will be based on the Primary Cohort dataset.
 
Once the target enrollment in the Primary Cohort is met, we will shift to direct enrollment into an Open-label Cohort. A screening period of up to 2 months will be followed by up to 18 months during which all participants will be assigned a 15mg/m²

----------------------------	--

dose and follow a similar pattern of procedures as the Primary Cohort during the open-label phase of the study. Participants will be followed for up to two months beyond the end of their open-label period. Because the rolling enrollment into the Open-label Cohort will result in variable duration of participation, the safety and biomarker data from the Open-label Cohort will not be used for the primary data analysis, although a secondary analysis of these data may be used for regulatory filings.

Descriptive statistics will be presented as counts and percentages for categorical variables, counts and ranges for events, and means with standard deviations, medians, and ranges for continuous variables. For safety and tolerability measures, we will consider clinical, rather than statistical, significance. Initial determinations will be made by the independent medical safety monitor physician familiar with the study population and blinded to treatment allocation.

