For modeling and inferential tests, we will consider a p-value less than 0.1 to be significant if the magnitude and precision of the estimated effect support that conclusion. Covariates will be specified in the description below. We will perform extensive exploratory data analysis and checks of model fit and will transform variables with obvious departures from normality.

Analysis of primary endpoints

Safety Analysis

Comparisons of participants experiencing treatment-emergent adverse events and clinically-significant abnormalities on clinical labs will be reviewed for clinical significance in the Safety Analysis dataset, which includes all participants who consume at least one dose of the study product. Events expected as part of the usual disease course in PKAN, whether present at trial enrollment or not, will not be considered or captured as adverse events.

Frequencies of participants experiencing at least one adverse event (AE) will be displayed by body system and preferred term according to *Medical Dictionary for Regulatory Activities* (MedDRA) terminology. Detailed information collected for each AE will include a description of the event; duration; whether the AE meets criteria as a Serious Adverse Event (SAE); severity / grade of the event; relationship to study product; changes made to the study product in response to the AE /SAE; and clinical outcome. Severity of the AEs will be graded according to the NCI *Common Terminology Criteria for Adverse Events*, Version 4.0. If the event meets criteria as an SAE, the nature of the SAE will be classified using standard FDA criteria.

The number and percentage of patients who experienced any serious AE (SAE), treatment-emergent AE, and treatment-emergent SAE will be summarized, as well as the total number of events per arm. AE data will be presented for months 0-6 and 7-37 and cumulatively, as appropriate. Emphasis in the analyses will be placed on AEs classified as treatment-emergent.

Clinically-significant abnormalities on clinical labs will be tabulated similarly to AEs. The number and percentage of patients experiencing clinically-significant abnormalities will be compiled in summary tables to examine the distribution by collection month [0-1-3-6-7-9-12-18-24 (25) months for the Primary Cohort; and 0-1-3-6-12-18 (19) months for the Open-label Cohort].

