This will be a single site, phase 2, safety and tolerability trial of 4'-phosphopantetheine (4'-PPT), a downstream product of intermediary metabolism in children and adults with PKAN, a inborn error of vitamin B5 metabolism. An initial 6-month, dose-ranging, parallel-group, randomized, double-blind, placebo-controlled phase will be followed by an 18-month, single-dose, open-label phase. There will be up to 2 months for screening and up to 2 months for follow up for up to a total of 28 months participation for this Primary Cohort. During the double-blind phase, participants in the Primary Cohort will be assigned randomly to one of three dose groups or placebo, with a 1:1:1:1 distribution. Once we meet our enrollment target for the Primary Cohort, we will shift additional enrollment directly into a single-dose open-label arm that will last up to 18 months per participant including up to 2 months for screening and up to 2 months for follow up. Our primary hypothesis is that there will be no clinically significant difference in safety or tolerability profiles between active and placebo groups during six months of double-blind parallel-group study, nor between dose groups over up to 18 months of treatment with 4'-PPT. Safety measures will include treatment-emergent adverse events collected at 10 time points and abnormalities on standard laboratory tests collected at 9 time points over 25 months (including follow up) for Primary Cohort participants. For the Open-label Cohort, treatment-emergent adverse events will be collected at up to 7 time points and safety labs at up to 6 time points over up to 20 months (including follow up). Participants will be stratified by PKAN type: classic or atypical, to ensure approximately equal distribution in each arm.

As a secondary, “proof of concept” aim, we will assess the pharmacodynamic profile of CoASY mRNA expression in the peripheral blood of participants receiving 4'-PPT or placebo. We will measure CoASY mRNA expression at 8 time points for the Primary Cohort and at up to 6 timepoints for the Open-label Cohort to examine four secondary hypotheses:

- a. **CoASY mRNA expression levels will rise in all 4'-PPT-treated participants after 1 month of treatment** compared with placebo-treated participants.

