Because PKAN is an ultra-rare disease, we are limited to 64 participants (15 in each arm + 4 potential dropouts allowing for 5% loss to follow-up) whom we will recruit from our established research registry, (prioritizing those participating in our "PKANready" ongoing natural history study) as well as by methods described within the protocol. This will be designated the "Primary Cohort". When our double-blind enrollment goal is met, enrollment of up to 86 additional participants will shift to an open-label arm; this will be designated the "Open-label Cohort". Enrollment into this cohort will be rolling, and thus the duration of follow up will vary based on the point of entry in the overall life of the

study. Our primary objective is to estimate effects of the study product and we will prioritize effect sizes over statistical power in interpreting results. Still, we wish to include sufficient numbers to estimate effects in our secondary and exploratory analyses of CoASY mRNA expression levels with some precision. In preliminary cross-sectional data, we found that the mean CoASY delta Ct (dCt) measures were 1.4 standard deviations higher in classic PKAN children (n=8) than age-matched healthy controls (n=6) on the \log_2 scale, where higher dCt indicates lower CoASY activity (mean=17.39 vs 16.85, SD=0.39). We anticipate that participants at all three dose levels will resemble healthy controls after 3 ± 2 days, while the placebo group will show no change. We simulated this change from baseline for 12 participants per group. For the standard deviation, we performed one set of simulations using the upper limit of the 60% CI for the standard deviation (0.34-0.48) as a conservative estimate. We regressed the dCt value on four indicator variables for study arm after treatment, with the intercept representing the common mean baseline value, and included a random intercept to induce correlation between paired measurements. We then used a Wald test for $\beta_{\text{placebo1}} - (\beta_{\text{low1}} + \beta_{\text{mid1}} + \beta_{\text{high1}})/3 = 0$ at $\alpha=0.05$. Pooling over 1000 simulated datasets, we find that we reject the null in 85-95% of simulations, approximating power to detect this difference at one month between the active and placebo groups.

b. Statistical plan for primary and secondary aims

Safety Analysis

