Comparisons of participants experiencing treatment-emergent adverse events and abnormalities on clinical labs will be reviewed for clinical significance in the Safety Analysis dataset, which includes all participants in the primary cohort who consume at least one dose of the study product. Events expected as part of the usual disease course in PKAN, whether present at trial enrollment or not, will not be considered or captured as adverse events.

Frequencies of participants experiencing at least one adverse event (AE) will be displayed by body system and preferred term according to *Medical Dictionary for Regulatory Activities* (MedDRA) terminology. Detailed information collected for each AE will include a description of the event; duration; whether the AE meets criteria as a Serious Adverse Event (SAE); severity / grade of the event; relationship to study product; changes made to the study product in response to the event; and clinical outcome. Severity of the AEs will be graded according to the NCI *Common Terminology Criteria for Adverse Events*, Version 4.0^[15]. If the event meets criteria as an SAE, the nature of the SAE will be classified according to standard FDA criteria.

The number and percentage of patients who experienced any serious AE (SAE), treatment-emergent AE, and treatment-emergent SAE will be summarized, as well as the total number of events per arm. AE data will be presented for months 0-6, 7-25 and cumulatively, as appropriate. Emphasis in the analyses will be placed on AEs classified as treatment-emergent.

Clinically-significant abnormalities on clinical labs will be tabulated similarly to AEs. The number and percentage of patients experiencing clinically-significant abnormalities will be compiled in summary tables to examine the distribution by collection month [0-1-3-6-7-9-12-18-24 +/- 25 months for the Primary Cohort; and 0-1-3-6-9-12-18 +/- 19 for the Open-label Cohort].

Graphic displays may be provided to illustrate the results over time. Initial review of group differences and determination of clinical significance will be performed by an unaffiliated physician familiar with the study population and blinded to treatment arm.

Tolerability Analysis

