We will compare the number of participants retained in each arm at each of the follow-up time points [0-(0+1week)-1-3-6-(6M+1week)-7-9-12-18-24-25 months for the Primary Cohort; and 0-(0+1week) -1-3-6-9-12-18-19 for the Open-label Cohort], taking into account whether dropout seems plausibly related to study participation and the mean percent of study product consumed. High retention in the study and product consumption per-protocol will be considered evidence of tolerability.

Analysis of secondary endpoints

We will estimate a CoASY pharmacodynamic profile in response to different doses of the study product in the Per-Protocol dataset. CoASY mRNA expression levels are continuous, measured in normalized differences in cycle times (ΔCt) on the \log_2 scale. Lower ΔCt indicates higher expression levels. We will use regression models controlling for PKAN type to estimate mean levels by treatment arms, including mixed effects when modeling over multiple time points.

To estimate the **change in expression levels after 3±2 days of treatment compared to placebo**, we will use a mixed effects regression model of the form $CoASY_{ijt} = \beta_0 + \beta_{jt}I(group = j)I(time = t \text{ and } t > 0) + \alpha I(cPKAN) + b_i$, $j = \text{placebo, low, mid, high}$; $t = 1$. Each individual contributes two observations (baseline and after); b_i represents the random intercept for subject. Baseline, represented by β_0 , is constrained to be the same for all groups because of randomization. Our primary approach will treat time as binary (0=baseline, 1=treated), though this can later be expanded to capture differences between days 1-5 of treatment. The β_{jt} represent mean changes from baseline for the three dose groups and placebo. An indicator for PKAN type (cPKAN or aPKAN) is included to reflect its role in stratified randomization. We will review regression coefficients as estimates of the magnitude of effect and test $\beta_{\text{placebo}1} - (\beta_{\text{low}1} + \beta_{\text{mid}1} + \beta_{\text{high}1})/3 = 0$ with a two-sided alpha of 0.1 to determine whether CoASY mRNA expression levels rose in all the study product-treated participants after initiation of treatment compared to placebo.

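### The safety laboratory endpoint is analysed only as a judged yes/no count per collection month: no within-participant comparison with screening, no active-placebo estimate of lab values, and no rule for pre-existing abnormalities

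*Combined protocol and SAP*

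**What the plan says.** The synopsis (Primary Outcome) and protocol section 2 define the safety endpoint as "treatment-emergent adverse events and abnormalities on standard laboratory tests". Laboratory findings are therefore part of the primary endpoint.

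The analysis is given in the synopsis (Statistical Methods, Safety Analysis) and in protocol section 10.b. Both say "Clinically-significant abnormalities on clinical labs will be tabulated similarly to AEs" and continue: "The number and percentage of patients experiencing clinically-significant abnormalities will be compiled in summary tables to examine the distribution by collection month". The months listed for the Primary Cohort run from 0 to 24, with 25 as an addition. A physician outside the study team, who does not know the arm, judges clinical significance. No grade, cut-off or baseline rule is given for that judgement.

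Four other provisions bear on this:

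- The synopsis (General approach) says "For safety and tolerability measures, we will consider clinical, rather than statistical, significance".
- The same paragraph offers means, SDs, medians and ranges for continuous variables in general, without tying them to on-treatment labs or to change.
- Section 10.b makes graphs over time optional.
- Section 10.d compares baseline lab measurements between groups descriptively and lists safety events by participant, measure and time point.

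The Schedule of Activities draws the metabolic profile and blood count at Screening and at Months 1, 3 and 6 of the blinded phase. No safety labs are drawn at the Baseline call, so the month 0 column must be the screening sample.

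**The concern.** Section 13.a states that the product is new to humans. In that setting the laboratory data should show whether liver, renal or blood values move on treatment. A count of judged abnormalities uses little of what is collected. It ignores any movement that stays below the judged threshold, and it does not separate a new abnormality from one the participant brought into the trial. The month 0 column gives the number abnormal per arm at screening, but not whether the person flagged at Month 3 is the person flagged at month 0.

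The choice also sits oddly with the plan's own aims. Section 10.a says that estimating effects matters more than power, and section 10.b plans a baseline-anchored model adjusted for PKAN type for CoASY, a secondary endpoint. The primary laboratory endpoint gets no effect estimate. At stake is whether a clean table with 15 placebo participants would be read as evidence of safety when it says little about moderate shifts.

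**Working it through.** **Inputs from the documents.** Section 10.a gives "15 in each arm + 4 potential dropouts allowing for 5% loss to follow-up"; as a check, 60/0.95 = 63.2, which rounds up to the stated 64. Section 5 allocates "with a 1:1:1:1 distribution", so the comparison is 15 placebo with 45 pooled active. The yardstick of 0.10 comes from the synopsis ("For modeling and inferential tests, we will consider a p-value less than 0.1 to be significant") and its two-sided form from the CoASY analysis ("with a two-sided alpha of 0.1"). The documents give no power, lab SD or cut-off for labs, so there is no stated laboratory figure to reproduce.

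**Assumptions.** A normally distributed analyte, one visit, a true shift of 1 SD on active, and a cut-off *c* in SD units above the placebo mean. The correlation *r* between screening and on-treatment values is taken from 0 to 0.7.

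**Counts.** The proportion flagged is 1 − Φ(c) on placebo and 1 − Φ(c − 1) on active. Power is exact for Fisher's test. The last column is P(at least 4 of 45 active) × P(at most 1 of 15 placebo), a rough stand-in for a gap that a reader of the table would notice.

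| Cut-off | Placebo | Active | Expected flagged, placebo / active | Power at 0.10 | Visible gap |
|---|---|---|---|---|---|
| 95th centile | 5.0% | 26.0% | 0.7 / 11.7 | 50% | 83% |
| 97.5th centile | 2.5% | 16.9% | 0.4 / 7.6 | 24% | 91% |
| 2.5 SD | 0.6% | 6.7% | 0.1 / 3.0 | 0.3% | 35% |
| 3 SD | 0.1% | 2.3% | 0.02 / 1.0 | about 0 | 2% |

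At 3 SD the chance that no active participant is flagged is (1 − 0.0228)^45, about 36%.

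**Screening-adjusted value.** In SD units, SE = √[(1 − r²)(1/45 + 1/15)], power = Φ(1/SE − 1.645), and the 90% interval has half-width 1.645 × SE.

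| r | SE | Power | Half-width |
|---|---|---|---|
| 0 | 0.298 | 96% | 0.49 SD |
| 0.5 | 0.258 | 99% | 0.42 SD |
| 0.7 | 0.213 | 99.9% | 0.35 SD |

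For a single dose against placebo (15 v 15), counts give 33%, 17% and 1.4% at the first three cut-offs; the value gives 86-99% over the same range of *r*.

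**Sensitivity to one visit.** If a participant is counted when abnormal at any of Months 1, 3 and 6 (assumed between-visit correlation 0.5 to 0.7), count-based power rises to 60-69% at the 97.5th centile and 11-19% at 2.5 SD.

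**Pre-existing abnormalities.** With no product effect, a 97.5th-centile cut-off and an assumed within-person correlation of 0.5 to 0.9, 18-59% of on-treatment abnormal values were already abnormal at screening. How far this unbalances the arms depends on prevalence, which is also assumed:

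| Prevalence at screening | Placebo and active differ by 15 points or more | Some two arms differ by 3 or more of 15 |
|---|---|---|
| 2% | 0.3% | 1% |
| 5% | 2.7% | 12% |
| 10% | 10% | 39% |
| 20% | 22-23% | 65% |

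The higher rows suit a count of any abnormal analyte. The rates used in the power table correspond to about 5% or less per analyte, where imbalance is uncommon.

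**The case against.** The strongest reply is that the plan intends no test on labs. Safety is judged clinically, so power is the wrong measure. Read as a table, 7.6 expected of 45 against 0.4 of 15 at the 97.5th centile would catch a reviewer's eye. This stands: the power figures measure information lost, not an error rate of the trial. It does not help at 2.5 or 3 SD, and a judgement of clinical significance may well lie beyond the normal limit.

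Second, a reader might infer that the plan ignores screening values, or that it counts pre-existing abnormalities as on-treatment findings. The documents support neither. Month 0 is a column in the same table, baseline labs are compared by group, listings allow a participant to be followed by eye, and tabulation modelled on AEs, where the emphasis is on treatment-emergent events, could let the physician set old abnormalities aside. The plan is silent on the rule.

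Third, continuous summaries are not excluded. That is true, but the general sentence commits to no change from screening and no comparison between arms, and the graphs are optional.

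Fourth, the 96-99.9% is idealised. Eligibility runs from 3 months to 89 years, samples go to local laboratories (mostly one company), and the figure pools three doses. A 1 SD shift inside the normal range may also have no clinical importance. All of this stands. It argues for presenting estimates to clinicians rather than tests, not for leaving the estimates out.

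**Conclusion.** The concern holds in a limited form. The specified laboratory analysis is a judged count per collection month. It has no individual-level comparison with screening, no active-placebo estimate of lab values and no stated handling of pre-existing abnormalities. For a 1 SD shift at one visit, the count retains at most 50% power over the cut-offs tried, against 96-99.9% for the adjusted value.

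These figures rest on normality, an assumed cut-off, an assumed correlation and a yardstick test that the plan does not use. It would go too far to say that a 1 SD shift is likely to be missed: with a cut-off at the normal limit it would probably be visible, and with one at 2.5 SD or more it probably would not. It would also go too far to say that baseline imbalance is likely to mislead, because that depends on a prevalence the documents do not give. The plan should be changed, since a better analysis is available from data already collected, but the trial does not fail without it.

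**What to change.** Add to the Safety Analysis in section 10.b and the synopsis:

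- For each analyte at Months 1, 3 and 6, report the active-minus-placebo difference in change from screening, adjusted for the screening value and PKAN type, with a 90% interval. Give the pooled active comparison and each dose.
- Show shift tables by arm from screening grade to worst on-treatment grade. CTCAE v4.0 is already adopted for AEs and can be extended to labs; for an analyte it does not grade, use the reporting laboratory's normal range.
- Define an emergent lab abnormality as a worsening from the participant's own screening grade, and state that an unchanged pre-existing abnormality is not counted as emergent.
- Keep the table of clinically significant abnormalities alongside.

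The cost is SAP wording and programming, with no new visits or samples. The downside is that many analytes at three visits will produce some differences by chance, and the age range and local laboratories add noise. The results should therefore be presented as estimates for clinical review, not as tests.
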